#### 8.7.7 ANTICIPATED ADVERSE EVENTS

Anticipated AEs associated with cataract surgery and/or premium IOL implantation that might reasonably be expected to occur in this study are listed below and include, but are not limited to, the following:

##### Intraoperative Adverse Events

- Anterior capsule tear
- Hyphema obscuring the surgeon's view
- Vitreous prolapse
- Wound leak (positive Seidel)
- Posterior capsular rupture
- Choroidal detachment/hemorrhage
- Zonular dialysis
- Thermal injury (phaco burn)

## Postoperative Adverse Events

- Anterior uveitis (including iritis and iridocyclitis)
- Capsular block syndrome
- Choroidal detachment/hemorrhage
- Chronic anterior uveitis [anterior segment inflammation characterized by grade 1+ cell or greater that is persistent for greater than 3 months after surgery, or relapses in less than 3 months after discontinuation of therapy, or the subject is maintained on therapy for more than 3 months to control inflammation.]
- Corneal edema [corneal swelling (stromal or epithelial) resulting in BCDVA of 0.3 logMAR or worse at Visit 3 or later]
- Cystoid macular edema (CME) diagnosed by clinical exam and adjunct testing (eg. OCT or other method), resulting in BCDVA of  $\leq 0.3$  logMAR at Visit 3 or later
- Difficulty with tasks in dim light resulting in secondary surgical intervention
- Endophthalmitis (intraocular inflammation leading to diagnostic vitreous tap and use of intraocular antibiotics)
  - Flat anterior chamber with lens/cornea touch or a shallow chamber with iridocorneal apposition without lens/cornea touch
- Hypopyon
- Incorrect IOL power resulting in secondary surgical intervention
- Increased glare or halos
- Increased IOP (elevation of IOP  $\geq 10$  mmHg above the IOP measured at the Preoperative Visit to a minimum of 25 mmHg)
- Infectious keratitis
- IOL damage resulting in secondary surgical intervention
- IOL malposition resulting in secondary surgical intervention
- Iris or pupil damage
  - Best-corrected distance visual acuity loss of 2 lines (10 letters) or more on the ETDRS chart measured at or after postoperative Visit 4 compared to any prior postoperative visit
- Mechanical pupillary block (A shallowing of the anterior chamber due to obstruction of aqueous humor flow from the posterior to anterior chamber through the pupil by the crystalline lens, vitreous face, or implanted device)
- Multiple (or “ghost”) images
  - Chronic pain in the study eye, per subjective patient reporting, graded as  $\geq 4$  on the standardized pain rating scale (from 0 to 10), present greater than 3 months postoperative
- Reduced contrast sensitivity
- Retained lens material

- Rhegmatogenous retinal detachment (RD) (partial or complete RD associated with retinal tear)
- Secondary IOL intervention (reposition, exchange or removal)
- Synechiae formation
- Toxic anterior segment syndrome (TASS) (An acute, noninfectious inflammation of the anterior segment of the eye that develops within 24 to 48 hours after surgery, usually resulting in hypopyon and commonly presenting with corneal edema, and that improves with steroid treatment)
- Undesirable severe optical phenomena resulting in secondary surgical intervention

Early, low grade anterior chamber cell/flare, corneal edema, and increase in IOP can often be considered normal or expected after IOL surgery. They do not need to be reported as adverse events if they occur prior to 1 week postoperatively if they meet the following criteria:

- Anterior chamber cells or flare of grade 2 or less and requires no change in standard postoperative medication regimen (if it persists to 1 week or more it should be reported as an adverse event);
- Corneal edema of grade 2 or less that does not reduce acuity to 0.3 logMAR (20/40) or worse and does not require any change in standard postoperative medication regimen (If it persists to 1 week or more it should be reported as an adverse event);
- Increased IOP that is <10mm Hg above baseline or is < 25mmHg and requires no change in standard postoperative medications regimen or any other special treatment.

However, note that all secondary surgical interventions (and events that cause these interventions) and all events that have sequelae should be reported as adverse events, regardless of when they occur.

Note: Posterior capsular opacification (PCO) is NOT to be reported as an AE, per ISO 11979-7. YAG capsulotomies should be reported in the subject's case report form.

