### 2.3 RISK/BENEFIT ASSESSMENT

#### 2.3.1 KNOWN POTENTIAL RISKS

Potential complications accompanying cataract or IOL implant surgery may include the following:

1. Ocular infection (endophthalmitis, microbial keratitis)
2. Inflammatory reaction [e.g. uveitis, Toxic anterior segment syndrome (TASS), hypopyon]
3. Anterior capsular phimosis
4. Corneal edema
5. Corneal endothelial damage
6. Cystoid macular edema (CME)
7. Secondary surgical intervention (including, but are not limited to: lens repositioning, lens replacement, vitreous aspiration, iridectomy for pupillary block, wound leak repair, and retinal detachment repair)
8. IOL dislocation, tilt, decentration, luxation, rotation
9. Elevated intraocular pressure
10. Pupillary block
11. Posterior capsular opacification (PCO)
12. Chromatic aberrations
13. Dysphotopsia
14. Loss of visual acuity
15. Deviation from target refraction
16. Hyphema
17. Retinal detachment

18. Iris or pupil damage
19. Posterior capsular rupture
20. Vitreous loss
21. Wound leak (positive Seidel)

In addition to these risks associated with cataract surgery and IOLs in general, multifocal IOLs in particular have been associated with an increased risk of reduced contrast sensitivity and also dysphotopias such as halos and glare, potentially leading to secondary surgical interventions.

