#### 8.7.5 ADVERSE EVENT REPORTING

All AEs that occur during or after the Preoperative Visit through completion of study participation must be documented. Adverse events are collected from time of informed consent, and may be determined by evaluating the following in relation to the study subject:

- Observed or volunteered problems
- Complaints
- Physical signs and symptoms
- The occurrence of a medical condition during the study, which was absent at baseline
- The worsening of a baseline medical condition during the study

Each subject eye must be examined for the presence/absence of adverse events at all visits, whether scheduled or not. If an AE occurs, the first concern will be the safety and welfare of the subject; treatment should be provided as appropriate for the event.

AEs, regardless of causal relationship, must be assessed by the Investigator and recorded in the subject's CRF. AEs should be recorded in the form of a diagnosis, rather than signs and symptoms. Each AE must be described as ocular or non-ocular along with the following information: date of onset, date of resolution, severity, nature of the event (intermittent, continuous), action taken (none, medical and/or surgical), relationship to study device and surgical procedure, seriousness criteria and expectedness. Any medication or other intervention necessary for the treatment of an AE must be recorded on the appropriate eCRF. If the same type of AE occurs multiple times, each event should be recorded separately.

AEs will be documented beginning at the time of onset, and documentation must continue until recovery is noted. Events that are ongoing at the time of study exit should be followed until resolution or stabilization.

Ocular conditions or diseases noted during the Preoperative Visit that are chronic but stable and meet the inclusion/exclusions criteria should be recorded as Ocular History in the subject's case report form.

The worsening of a preoperative condition or disease will be considered an AE. As applicable, signs and symptoms indicating a common underlying pathology should be noted as one comprehensive event.

---

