#### 9.4.11 ADDITIONAL EFFECTIVENESS ANALYSES

All additional effectiveness analyses will be based on the All-implanted Analysis Set population unless otherwise stated.

The visual acuity exploratory endpoints are as follows:

- Photopic monocular logMAR BCDVA, [REDACTED], DCIVA (66 cm), and DCNVA in first operative eyes at Month 6 (Visit 4) and Month 12 (Visit 5)
- Mesopic monocular logMAR [REDACTED], DCIVA (66 cm), and DCNVA in first operative eyes at Month 6 (Visit 4) and Month 12 (Visit 5)
- Photopic binocular logMAR BCDVA, [REDACTED], DCIVA (66 cm), and DCNVA at Month 6 (Visit 4) and Month 12 (Visit 5)
- Mesopic binocular logMAR [REDACTED], DCIVA (66 cm), and DCNVA at Month 6 (Visit 4) and Month 12 (Visit 5)
- Photopic monocular logMAR UCDVA, [REDACTED], UCIVA (66 cm), and UCNVA in first operative eyes at Month 6 (Visit 4) and Month 12 (Visit 5)
- Photopic binocular logMAR UCDVA, [REDACTED], UCIVA (66 cm), and UCNVA at Month 6 (Visit 4) and Month 12 (Visit 5)
- Photopic monocular logMAR [REDACTED] and BCNVA in first operative eyes at Month 6 (Visit 4) and Month 12 (Visit 5)
- Photopic binocular logMAR [REDACTED] and BCNVA at Month 6 (Visit 4) and Month 12 (Visit 5)

A visual acuity variable will be summarized categorically by logMAR level by presenting the sample size, frequency, and percentage of subjects with logMAR visual acuity within the following visual acuity ranges:

- 0.00 logMAR or better
- 0.10 logMAR or better
- 0.20 logMAR or better
- 0.30 logMAR or better
- Worse than 0.30 logMAR

A visual acuity variable will be summarized categorically by Snellen level by presenting the sample size, frequency, and percentage of subjects with Snellen visual acuity within the following visual acuity ranges:

- 20/20^-2 or better: ≤ 0.04 logMAR
- 20/25 or better: ≤ 0.14 logMAR
- 20/32 or better: ≤ 0.24 logMAR
- 20/40^-2 or better: ≤ 0.34 logMAR
- Worse than 20/40^-2: > 0.34 logMAR

The visual acuity exploratory endpoints will be summarized categorically by logMAR level and Snellen level by treatment group and will also be summarized by treatment group using continuous descriptive statistics.

Additionally, photopic monocular logMAR BCDVA, DCIVA (66 cm), and DCNVA in first operative eyes at Month 12 (Visit 5) will be analyzed by repeating the primary and secondary effectiveness analyses at Month 12 (Visit 5).

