## **13. Effectiveness Analyses**

### **13.1 Primary Analyses**

The co-primary effectiveness endpoints are:

- Photopic monocular logMAR best corrected distance visual acuity (BCDVA) in first operative eyes at Month 6 (Visit 4)
- Photopic monocular logMAR near visual acuity with distance correction (DCNVA) in first operative eyes at Month 6 (Visit 4)

The primary analyses of the primary effectiveness endpoints will be based on the AAS with intercurrent events handled using the primary strategy presented in [Section 8.2](#).

If a subject has no observed data for an endpoint at any of the scheduled visits (e.g. subject exits study prior to Month 1 [Visit 3A] study visit and therefore has no DCNVA data), the endpoint will be imputed at the earliest scheduled visit as a normal random variable with mean equal to the respective treatment group mean and SD equal to the respective treatment group SD based on observed data for the respective treatment group at the earliest scheduled visit for that endpoint. If the imputed value is less than the minimum observed value within the respective treatment group or greater than the maximum observed

value within the respective treatment group, the imputed value will be set equal to the minimum or maximum value, respectively. This initial imputation procedure will be performed for BCDVA using SAS® code similar to the code below:

```

proc means data = indata noprint;
  var base;
  by trt;
  output out = A3_stats(drop = _TYPE_ _FREQ_) mean = mean std
= sd min = min max = max;
run;

data indata(drop = mean sd min max Z);
  call streaminit(938428);
  merge indata indata_stats;
  by trt;

  if cmiss(base, aval_v2, aval_v3, aval_v4, aval_v5) = 5 then
do;
  Z = round(rand('Normal', mean, sd), 0.02);
  if Z > max then Z = max;
  else if Z < min then Z = min;
  base = Z;
end;
run;

```

where

- trt = treatment group coded as 1 for the test IOL and 2 for the control IOL
- base = BCDVA at baseline
- aval\_vi = BCDVA at Visit i, i = 2, 3, 4, and 5.

Similar code as above will be used for DCNVA with "base" replace by "aval\_v3" in the means procedure block of code and the data step cmiss if-condition updated to "if cmiss(aval\_v3, aval\_v4, aval\_v5) = 3" and clause "base = Z" updated to "aval\_v3 = Z".

Non-monotone missing data for BCDVA will first be multiply imputed using treatment-based MCMC methodology similarly as in the SAS® code below:

```

/* Impute non-monotone missing data using treatment-based MCMC

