### 13.1.1 SENSITIVITY ANALYSIS I

The sensitivity analysis described in this section will only be performed for BCDVA in first operative eyes at Month 6 (Visit 4) for the AAS. The handling of intercurrent events will be updated as follows:

1. Withdrawal due to physician decision: missing data assumed to be MNAR. Treatment-based multiple imputations, *using the worst half of the subjects who have data within the same treatment group*, will be completed for non-inferiority hypotheses. [hypothetical strategy]
2. Missing data without withdrawal or withdrawal due to reasons other than due to physician decision: missing data assumed to be MAR. Treatment-based multiple imputations will be completed. [hypothetical strategy]

SAS® code similar to the code below will be used to identify the worst half of subjects for BCDVA by treatment group at Month 6 (Visit 4):

```

proc sort data = indata;
  by trt;
run;

proc means data = indata noprint;
  var aval_v4;
  by trt;
  output out = v4_median(drop = _TYPE_ _FREQ_) median =
median_v4;
run;

data indata(drop = median_v4);
  merge indata v4_median;
  by trt;

```

```

  if aval_v4 >= median_v4 then worse_median_flg = "Y";
  else worse_median_flg = "N";
run;

```

If a subject has no observed BCDVA data at any of the scheduled visits, BCDVA will be imputed at the earliest scheduled visit as described in [Section 13.1](#). Non-monotone missing data will first be imputed using treatment-based MCMC methodology as described in [Section 13.1](#).

After imputation of non-monotone missing data, the BCDVA data will be partitioned into a dataset containing missing data due to withdrawal due to physician decision and a data set containing the remaining BCDVA data, including missing data due to any other reason:

```

/* Split mcmc into cases where missing is due to withdrawal due
to physician decision or other */
data mcmc1;
  set mcmc (where = (DSDECOD ne "Physician Decision"));
run;

data mcmc2;
  set mcmc (where = (DSDECOD = "Physician Decision"));
run;

```

where

- DSDECOD = reason for discontinuation.

The monotone missing data not due to withdrawal due to physician decision will be imputed using treatment-based regression methodology using SAS® code similar to the code below:

```

/* Impute missing data not due to Physician Decision using
treatment-based regression methodology */
proc sort data = mcmc1;
  by trt _imputation_;
run;

proc mi data = mcmc1 out = mil nimpute = 1 seed = 891568 round =
0.02;

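### Does the reversed acuity sign in the protocol's cystoid macular edema entry affect any count, report or analysis?

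*Protocol*

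**What the plan says.** Protocol 8.7.7 (Anticipated Adverse Events) lists postoperative events, some with a qualifying acuity. The CME entry requires diagnosis by clinical examination and adjunct testing, with "BCDVA of $\leq 0.3$ logMAR at Visit 3 or later". The corneal edema entry in the same list reads "corneal swelling (stromal or epithelial) resulting in BCDVA of 0.3 logMAR or worse at Visit 3 or later". Later in 8.7.7, the exemption for early low-grade corneal edema applies only if the edema "does not reduce acuity to 0.3 logMAR (20/40) or worse".

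CME appears in three other places in the protocol, each time without an acuity limit: the known risks (2.3.1), the ISO cumulative events (8.7.2.1) and the ISO persistent events (8.7.2.2).

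Protocol 8.7.5 asks the investigator to record several attributes of each adverse event, including "relationship to study device and surgical procedure, seriousness criteria and expectedness".

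**The concern.** The two edema entries share a measure, a cut-off and a time point, yet their inequalities run in opposite directions. An entry that speaks of CME resulting in an acuity of 20/40 or better makes little sense as an event definition. It would admit eyes with normal vision and exclude the eyes in which CME has done visible harm.

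The stake would be inconsistent classification. Section 8.7.7 is the protocol's list of anticipated events, and sites must record expectedness. A site applying the entry literally could call vision-reducing CME unexpected, while a site relying on 2.3.1 would call the same event expected. The definition of an unanticipated adverse device effect (8.7.3) also turns on whether the protocol had already identified a serious effect in nature, severity or frequency. That status brings reporting duties to the IRB and FDA with a limit of 10 working days (8.7.6).

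**Working it through.** No sample size, power or error rate is involved. The check has two parts: the direction of the scale, and what depends on the entry.

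**1. Direction of the scale.** Four places agree that a higher logMAR is worse:
- Protocol 9.4.11 has acuity bands up to 0.30 described as that level or better, and then "Worse than 0.30 logMAR".
- SAP 13.1.1 picks out the worse half of subjects with the code "if aval_v4 >= median_v4 then worse_median_flg".
- SAP 16.1 equates a rise of at least 0.20 logMAR with a loss of at least 10 letters.
- Protocol 9.1 defines superiority in near and intermediate acuity as a negative difference, test minus control.

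**2. The two rules side by side.** Snellen denominator = 20 × 10^logMAR.

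| logMAR | Snellen | CME entry as printed (≤ 0.3) | Corneal edema entry (0.3 or worse) |
|---|---|---|---|
| 0.00 | 20/20.0 | met | not met |
| 0.20 | 20/31.7 | met | not met |
| 0.30 | 20/39.9 | met | met |
| 0.34 | 20/43.8 | not met | met |
| 0.40 | 20/50.2 | not met | met |
| 1.00 | 20/200.0 | not met | met |

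The value at 0.30 reproduces the 20/40 that 8.7.7 itself gives. The rules meet only at exactly 0.30. That is true of any pair of rules of the form ≤ x and ≥ x, so counting how many acuity values they disagree on says nothing about the effect on the trial.

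**3. What depends on the entry.**
- *Recording.* Protocol 8.7.5 requires every adverse event to be documented, whatever its cause. The early-event exemptions in 8.7.7 cover anterior chamber cells or flare, corneal edema and raised pressure, and not CME.
- *Status of the list.* Section 8.7.7 says that its list is not exhaustive, so an eye outside the literal wording does not become unanticipated for that reason.
- *ISO comparison.* The counts compared with the ISO rates (Protocol 9.4.6, SAP 15.2) use the ISO categories, in which CME has no acuity qualifier. SAP 15.2 counts cumulative events occurring at any time in the study and persistent events ongoing at exit.
- *Expedited reporting.* Under 8.7.6, ocular serious events and unanticipated device effects go to the sponsor within 24 hours whether expected or not.
- *Unanticipated device effects.* The test in 8.7.3 looks to the whole protocol. Section 2.3.1 lists both CME and loss of visual acuity without limit, and 8.7.7 separately lists a loss of 10 letters or more at or after Visit 4.
- *Summaries.* Protocol 9.4.6 and SAP 15.3 split adverse events by relationship, severity, seriousness, onset, age, site or investigator, and (in the SAP) pupil size. Neither describes a split by expectedness.

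**The case for a change.** The strongest case for acting is that the text is wrong on its face, that correcting it would cost one symbol, and that 8.7.7 is the only place where the protocol ties CME to an acuity level. Because 8.7.3 mentions severity, a strict reader could say that vision-reducing CME was never identified at that severity, and sites might then differ. Misreading of the PDF is also not an easy way out: in the same list the signs for raised pressure (≥ 10 mmHg) and chronic pain (≥ 4) came through sensibly.

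The inconsistency itself stands. Its consequence does not. The phrase about the edema resulting in a given acuity, together with the corneal edema entry in the same list, makes the intended direction plain to an ophthalmologist, and investigators assess these events with clinical judgement. If a site did follow the printed sign, the error would be to call vision-reducing CME unexpected, which invites more scrutiny of the event rather than less. Mild CME would be called anticipated, which 2.3.1 supports anyway.

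One link cannot be closed from the documents. Adverse events will also be summarised under the American Academy of Ophthalmology task force definitions (Protocol 9.4.6, SAP 15.3), which are not reproduced. The plan attributes those definitions to the task force publication and not to 8.7.7, so there is no stated route by which the sign would enter that summary.

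**Conclusion.** The CME and corneal edema entries in Protocol 8.7.7 contradict each other in direction, most likely through a typographical slip. This does not call for a change to the plan. No primary or secondary endpoint, ISO event count, hypothesis test, power figure or 24-hour reporting duty in the documents uses the CME threshold. Correcting it would alter no planned result.

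This rests on three assumptions: that the printed page carries the same symbol as the extracted text; that the case report form and Manual of Procedures, which are not available here, do not turn the 8.7.7 wording into a filter on which CME events are entered; and that the SAP's table shells, which are also not visible, add no summary by expectedness. If the protocol is reopened for another reason, the sponsor can check the symbol and reconcile the two entries as an editorial matter.

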#### 8.7.8 DEVICE DEFICIENCIES

Device deficiencies related to the identity (e.g., labeling), quality, durability, reliability, safety, effectiveness, or performance of the study device must be reported to the Sponsor, or Sponsor's designee, within 7 days of the Investigator becoming aware of the deficiency. Device deficiencies must be recorded in the subject's case report form.

Device deficiencies will be categories as one of the following:

- **Device failure:** A device has failed if it is used according to the labeling, including without limitation, instructions for use, and applicable standards of medical practice but does not perform according to the labeling and negatively impacts the treatment.
- **Device malfunction:** A device malfunction is a change in the function of the device that is not

described in the labeling and that may or may not affect device performance.

- **Device misuse:** A misused device, i.e. one that is not used by the Investigator (in the study) in compliance with applicable standards of medical practice, including without limitation, those described in the instructions for use and labeling, will not be considered a malfunction.
- **Other:** must be described by the Investigator

## 9 STATISTICAL CONSIDERATIONS

### 9.1 STATISTICAL HYPOTHESES

#### Primary Effectiveness Hypotheses

The null and alternative hypotheses for the first co-primary effectiveness analysis are:

$$H_{01e}: \mu_{t1e} - \mu_{c1e} \geq 0.10$$

$$H_{11e}: \mu_{t1e} - \mu_{c1e} < 0.10$$

Where  $\mu_{t1e}$  and  $\mu_{c1e}$  denote the population mean photopic monocular BCDVA (logMAR) at 4m in the first operative eyes at Month 6 (Visit 4) for the test and control IOLs, respectively.

The null and alternative hypotheses for the second co-primary effectiveness analysis are:

$$H_{02e}: \mu_{t2e} - \mu_{c2e} \geq 0$$

$$H_{12e}: \mu_{t2e} - \mu_{c2e} < 0$$

Where  $\mu_{t2e}$  and  $\mu_{c2e}$  denote the population mean photopic monocular DCNVA (logMAR) at 40 cm in the first operative eyes at Month 6 (Visit 4) for the test and control IOLs, respectively.

